#### 8 DATA COLLECTION & MANAGEMENT

#### 8.1 DATA COLLECTION

It is the CI's responsibility to ensure the accuracy of all data entered and recorded in the CRFs, the database and spreadsheets. The Delegation of Responsibilities Log will identify all study personnel responsible for data collection, entry and discrepancy management.

The paper CRF, designed by TCTU and approved by the CI, Statistician and Health Economist, will be issued to sites following site activation. Competed CRFs will be stored in a secure, restricted access storage facility.

The data will be collected by the RN, or other delegated person and/or the Site PI and entered into a paper CRF. Information will then be transferred contemporaneously (and within a maximum of 10 working days), by delegated staff, to the web-based study electronic database run in OpenClinica or

the PMS hosted by HIC. Delegated staff will carry out visual verification of data entered from CRF to OC; this quality control activity will be logged and a copy provided to the trial manager / delegate for review. All research data and data established from the NHS tests will be stored in an unidentifiable format on this secure, password protected database hosted by HIC, University of Dundee.

The PMS will be updated by delegated staff; this will provide co-primary outcome recruitment data. Screening activity will be entered onto the Screening Activity Excel spreadsheet; this will be updated and provided each month to the Trial Manager / delegate.

To preserve blinding the follow-up Oral Iron Use Scale (oral iron only), iron treatment and Participant Experience and Views questionnaires will be quarantined. The unblinded RN will transfer the Oral Iron Use Scale and iron treatment data onto version controlled Excel spreadsheets. LabKey will be used to securely upload the Excel Oral Iron Use Scale and iron treatment data files and Participant Experience questionnaires. Following data lock these data will be analysed separately from the main dataset; by the Health Economics Research Unit (HERU) based in the University of Aberdeen.

The medical notes or electronic health records will provide source data for past medical history, prescriptions, subsequent medical conditions, hospital admissions, diagnostic reports and blood results.

NOTE: To preserve blinding, the blinded RN should avoid reviewing the medical record until followup outcome assessments have been completed.

The CRF and study questionnaires will be used as source data, where appropriate, and data relevant to a participant's general medical history will also be recorded in their case notes.

Following database lock HIC will perform NHS data linkage for the Fife site only, for cross-validation purposes. Established over 10 years ago, HIC is recognized as a leader in health data linkage (25), and were the first centre in Scotland to offer a Safe Haven, this is Nationally Accredited and ISO27001 certified. Operating under tight data governance controls, the Safe Haven allows secure collaborative research using sensitive eHealth data.

HIC maintains a clinical data repository of eHealth data covering approximately 20% of the Scottish population. The eHealth repository combines routine collected datasets for the Tayside and Fife population and Tayside, with local speciality research, and clinical datasets. All HIC's clinical datasets are fully indexed and electronically linkable.

The following routinely collected NHS data will be obtained:

- o medication prescription data to assess medication adherence
- hospital record (SMR 00 Outpatients; SMR01 Inpatients and Day Cases) and GP attendance data to assess health care use.

These data will be pseudo-anonymised as per HIC SOPs.

The cross-validation dataset will be securely accessed via the HIC Safehaven. This data will be provided within a separate file, and not imported into the OpenClinica database.

Statistical modelling will be used for other sites.

#### 8.2 DATA MANAGEMENT SYSTEM

The web-based PMS / recruitment tracker hosted by HIC, University of Dundee, will be designed to capture and report the co-primary outcomes. Formal / documented User Acceptance Testing will be carried out by TCTU prior to the CI conducting a review and system approval (prior to release of the live system).

The web-based data management system, OpenClinica (OC), will be provided and managed by TCTU, University of Dundee using a GCP compliant system. The Screening Activity and Oral Iron Use Scale (oral iron only) and iron treatment Excel spreadsheets will be created and provided by TCTU. OC and the Excel Oral Iron Use Scale and iron treatment databases will be based on the protocol and the CRF. All databases will be subject to formal / documented User Acceptance Testing and the CI / delegate will conduct a review to ensure that OC database, the Excel Oral Iron Use Scale and iron treatment spreadsheets match the CRF; prior to release of the live OC database and Excel spreadsheets the CI will approve the systems. OC database and Excel spreadsheet version changes will be managed as per TASC SOPs. The CRF, OC and Excel spreadsheets will not collect more information than is required to meet the aims of the study and to provide evidence of eligibility and safety of the participant.

The NHS Fife prescribing and health and social care use data (for data linkage) will be obtained and processed by HIC following OC database lock. This will be stored within a separate database on the NHS Tayside Safehaven.

Any queries will be resolved by the Investigator or delegated member of the study team. TCTU will generate and issue data query forms; following source data review sites will provide response,

update CRF and OC. Queries will be issued to sites throughout the study, with the aim of completing database lock within 3 months of the last patient last visit.

Password protected access and use of PMS, OC, data spreadsheets and Safehaven will be restricted to relevant research team members; will be granted for study monitoring purposes.

Development and validation of the study database and QC and extraction of data will be carried out according to TASC procedures and SOPs; records of these activities will be filed within the Data Management section of the TMF. Extracts for analysis will be managed by TCTU and based on the Statistical Analysis Plan (SAP).

The Data Management Plan and SOPs will provide details of the system and processes.

#### 9 STATISTICS AND DATA ANALYSIS

#### 9.1 SAMPLE SIZE CALCULATION

Since this is a pilot study, under CSO guidance, no formal sample size calculation is provided – indeed this pilot study will furnish indicative data to allow a sample size calculation for the full trial. We will aim to have 20 completed participants in each arm (60 in total). The target is set at 20 completed participants per arm so as to have sufficient variability in response to provide estimates for future sample size calculation. We also would like to have a sufficient number to examine the feasibility of the recruitment pathways we are proposing. It is also in line with current practice in which a pilot study sample size is ~40-50 for a two-arm trial. Assuming a dropout rate of 30%, we therefore plan to recruit and randomise a total of 84 participants. We will recruit for a maximum of 15 months at four sites (total target N=84).

Linked NHS Fife prescribing and health and social care use data will used for statistical modelling; this will use data from a maximum of 21 participants. Our aim is to test the process of obtaining linked data and to conduct preliminary data verification to inform the main study; to obtain standard deviation and mean outcome variables and to calculate the sample size for the main study and not to obtain statistical results of significance.

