#### 4 STUDY POPULATION

#### 4.1 NUMBER OF PARTICIPANTS

Community dwelling people aged 65 years or over who meet the following study eligibility criteria and reside within the catchment area of participating NHS organisations. A total of 84 participants (approximately 21 in each NHS site i.e. 7 participants randomised into each study arm) will be recruited into the study.

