#### 5.5 RANDOMISATION

#### 5.5.1 Randomisation

After successful screening for eligibility and safety, and completion of baseline outcome measures, participants will be randomised on a 1:1:1 allocation ratio via a web-based system TRuST, run by the Tayside Clinical Trials Unit (TCTU) and hosted by HIC, to preserve allocation concealment. The TRuST system will be based on the study protocol; system validation and User Acceptance Testing will follow HIC and TASC SOPs; CI review and approval will be carried out prior to the live system release.

The study arms are:

- Continue oral iron
- Stop oral iron
- Stop oral iron and give IV iron (as per local formulary).

Direct care physicians (i.e. GP or hospital clinician) will receive written notification of the randomisation allocation. Participants will be verbally informed of treatment allocation (telephone visit). Treatment allocation will be recorded in the participant medical record.

Where web-access is not possible at site, emergency randomisation will be provided by TCTU via [contact]; following the TCTU Unblinding Work Instruction. Verbal notification of randomisation will be provided; email record of emergency randomisation will be provided when web-access is available) and filed in the participant medical record.

A minimisation algorithm with a random element will be used to ensure balance across recruitment centres and key baseline measures. Randomisation will be stratified by site, and further balanced using minimisation. Haemoglobin after minimum 8 weeks of oral iron (>=100g/L vs <100g/L), ferritin prior to commencement of oral iron (>=50ug/L vs <50ug/L) and six minute walk distance (>=300m vs <300m) will be the minimisation variables.

Only those involved with development and maintenance of the system will have access to the treatment allocations during the study; those involved with outcome assessment or statistical analysis will not have access to allocation until the point of the final analysis after database lock. Unblinding will occur following OC database lock; the CI will formally request unblinding.

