#### 5.5.2 Withdrawal procedures

Participants will be withdrawn from the study if a) they request to withdraw, or b) they lose capacity to give informed consent (as assessed by the clinical judgement of the local PI/delegate). Withdrawal will be as per Sponsor SOP and documented using the Sponsor Withdrawal Form.

Any physician, involved in direct care (i.e. GP or hospital clinician) or study care (i.e. PI/ medically qualified delegate), using their clinical judgement may withdraw a study participant from their randomised treatment. This may occur due to the occurrence of:

- an adverse event (AE)
- the onset of a symptom that is deemed related to the study participation or related procedures
- the onset of a symptom that is an exclusion criteria
- any other reason which in their clinical judgement requires the participant to be withdrawn

Patients withdrawn from randomised treatment will remain in the study (with consent) for safety follow-up and outcome measures, and will be included in the intention to treat analysis (ITT) but will be censored in per-protocol analyses. If withdrawal is due to a study intervention product related AE it will be logged as such on the Adverse Event Log. All reasons for withdrawal will be noted in the participant's CRF and medical notes.

If at any time the participant formally withdraws his/her consent for future participation and disclosure of future information, no further evaluations will be performed and no additional data will be collected. With consent, data collected before withdrawal will be retained and used in the study analysis; where withdrawal includes data, and if this occur before data base lock, the data will be excluded from analysis. Although a participant is not obliged to give reason(s) for withdrawing consent prematurely, if the participant appears lost to follow up, the CI will make a reasonable effort to ascertain the reason(s), while fully respecting the individual's rights, and will demonstrate that everything possible was done in an attempt to find any participant lost to follow-up. Those lost to follow-up or withdrawn will be identified and a descriptive analysis of them provided, including the reasons for their loss and its relationship to treatment and outcome.

A dropout rate of 30% is assumed, we therefore aim to recruit and randomise up to 84 participants to ensure that we have 20 completed participants per treatment arm (60 in total).

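### At the stated 30% dropout, 84 randomised gives an expected 58.8 completers (19.6 per arm), slightly short of the 60 (20 per arm) that Section 5.5.2 says it will ensure

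*Protocol*

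**What the plan says.** Section 9.1 sets the target as an aim: "We will aim to have 20 completed participants in each arm (60 in total". It then moves from target to number randomised: "Assuming a dropout rate of 30%, we therefore plan to recruit and randomise a total of 84 participants". The inference word in that sentence presents 84 as the result of inflating 60 for 30% dropout.

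Section 5.5.2 repeats the 30% assumption and says the team will "aim to recruit and randomise up to 84 participants to ensure that we have 20 completed participants per treatment arm (60 in total". Two things differ from Section 9.1. The 84 becomes an upper limit rather than a total, and 20 completers per arm becomes something ensured rather than aimed for.

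Section 5.5.1 states that "participants will be randomised on a 1:1:1 allocation ratio", which makes 28 per arm if 84 are randomised. Section 4.1 describes the same total as "approximately 21 in each NHS site i.e. 7 participants randomised into each study arm", that is 4 sites × 3 arms × 7. Section 9.1 also says that "no formal sample size calculation is provided", because this is a pilot.

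**The concern.** A number inflated for dropout should return at least the target when the assumed dropout is applied to it. Here it does not: 30% off 84 leaves fewer than 60. Section 5.5.2 goes further by treating a ceiling on recruitment as a guarantee of a minimum number of completers.

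What is at stake is how the pilot will read against its own plan. Dropout at 3 months is a secondary outcome (Section 2.2.2), to be tabulated with a 95% confidence interval (Section 9.2). If 25 of 84 drop out, that is 29.8%, no worse than assumed, yet 59 complete and the stated target is missed. A reader would see a retention shortfall that comes only from rounding in the plan.

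**Working it through.** **Inputs**
- Target: 20 completers per arm, 60 in total (Sections 9.1 and 5.5.2).
- Assumed dropout: 30% (both sections).
- Number randomised: 84 (Sections 4.1, 5.5.2 and 9.1).
- Allocation 1:1:1 (Section 5.5.1), so 84/3 = 28 per arm.

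**Step 1. Reproduce the plan's figure.** Number to randomise = completers/(1 − dropout).
- In total: 60/0.70 = 85.7, rounded up to 86.
- Per arm: 20/0.70 = 28.6, rounded up to 29, so 3 × 29 = 87 with equal arms.
- The plan has 84: 2 fewer than 86 (2/84 = 2.4%) and 3 fewer than 87 (3.6%).
- The common mistake of multiplying by (1 + dropout) would give 60 × 1.30 = 78. That is not what was done. The plan's figure is close to the correct inflation but on the low side.

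**Step 2. Apply the plan's dropout to the plan's number.**
- In total: 84 × 0.70 = 58.8, which is 1.2 below 60.
- Per arm: 28 × 0.70 = 19.6, which is 0.4 below 20.

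**Step 3. Find the dropout at which 84 does meet the target.**
- 1 − 60/84 = 24/84 = 28.6%. At most 24 may drop out in total.
- Twenty in every arm of 28 means at most 8 dropouts in each arm (8/28 = 28.6%).

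**Step 4. Check what rounding up would give.**
- 87 × 0.70 = 60.9 in total and 29 × 0.70 = 20.3 per arm: the target is met in expectation.

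**Step 5. Effect on the stated purpose.** Section 9.1 wants 20 per arm so that variability can be estimated for the definitive trial. Under normality the relative standard error of a standard deviation is about 1/√(2(n − 1)).
- n = 20: 1/√38 = 16.2%.
- n = 19.6: 1/√37.2 = 16.4%.

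The difference is 0.2 percentage points, too small to affect the planning of the main trial.

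**The case against.** The strongest reply is that this is rounding in a pilot that disclaims a formal calculation. An expected 19.6 rounds to 20, a dropout of 28.6% is close to a round 30%, and 84 fits the layout of four sites with 7 per arm. Section 9.1 says only that the trial will aim for 20, and the main verb in Section 5.5.2 is also *aim*. All of this stands as to size. It does not remove the point: both sections present 84 as following from 30% dropout, neither cites the site layout as the reason for the number, and Section 5.5.2 still uses the word *ensure*.

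Stronger readings are tempting, but the documents do not support them.
- *The pilot is materially too small, or its justification fails.* Twenty completers per arm is not the only reason given. Section 9.1 also cites having enough participants to examine the recruitment pathways, and agreement with usual pilot sizes. The co-primary outcomes, randomisation rate and proportion by recruitment route, depend on the number randomised and not on completers.
- *The chance of missing the target shows how serious the error is.* With independent dropout at exactly 30%, the probability that all three arms of 28 reach 20 is 0.15. With the correctly rounded 29 per arm it is still only 0.26. Low odds of this kind come mostly from random dropout and would remain after correct rounding. They are a reason not to promise a minimum, but they are not evidence of the rounding error.
- *Dropout will differ between arms and make the shortfall worse.* The protocol gives no arm-specific dropout figure, so nothing can be built on this.

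**Conclusion.** The point holds as a minor arithmetic and wording error. Under the protocol's own 30%, 84 randomised falls short of 60 expected completers by 1.2, or 0.4 per arm. Covering the target in expectation would take 86, or 87 with equal arms. Section 5.5.2 claims more than the design delivers, and it disagrees with Section 9.1 on both the strength of the target and whether 84 is a total or a limit.

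The consequences for the pilot's estimates and for its recruitment outcomes are negligible. The arithmetic assumes that the 30% applies equally to all randomised participants and that 1:1:1 allocation yields 28 per arm. Minimisation with a random element may leave the arms slightly unequal, which would not change the expected total of 58.8.

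**What to change.** Keep 84 and correct the statements built on it.
- In Sections 9.1 and 5.5.2, state: *With 84 randomised and 30% dropout, about 59 completers (19 to 20 per arm) are expected; 60 completers requires dropout of at most 28.6%.*
- In Section 5.5.2, replace *to ensure* with *aiming for about*.
- Describe the 84 in the same way in Sections 4.1, 5.5.2 and 9.1, as a total or as a maximum.

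The cost is two sentences and a slightly less favourable stated figure. No patients are added, and neither the design nor the analysis changes. Raising the number to 87 is not needed: the gain in precision would be trivial, and 87 would not guarantee 20 per arm either.

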#### 9.2 STATISTICAL ANALYSIS PLAN

All analyses will be by intention to treat, and will thus include all participants randomised. Data will be analysed by an independent statistician from Medical Statistics Team and a Research Assistant from HERU.

Baseline demographics and clinical characteristics will be presented as mean (SD), median (IQR) or percentage (n) as appropriate across study arms. Hb and ferritin level at 3 months will be compared across study arms using analysis of covariance with baseline Hb and ferritin level and site as covariates. Intra study arm comparisons will be assessed using the paired t-test or Wilcoxon signed rank test. Number of eligible patients per site, recruitment rate across sites, the proportions recruited by each method within site, dropout and crossover rates, all with corresponding 95% confidence intervals will each be tabulated. Effect size estimates of difference in Hb and ferritin level between arms will be calculated. The latest available SPSS version at the time of conducting statistical analysis will be used for analysis with intention to treat as the main analysis.

A per-protocol analysis will also be performed on completers of the study as a secondary analysis, primarily for safety outcomes (adverse event rates, falls).

Health economic measures (costs of healthcare use, comprising hospital stays for reasons related to

anaemia and outpatient/day case visits for iv iron administration, costs of blood transfusion and oral iron, and quality of life measurement using EQ-5D-5L and 15D) will be presented as unadjusted mean (SD) and median (IQR) values. Regression-based adjusted costs and quality of life values will also be calculated, with baseline cost, quality of life values, treatment group and patient demographics as co-variates. The percentage of missing data per resource use item and per quality of life questionnaire will also be presented.

We will assess both feasibility of secondary outcome measures and distribution of changes; these data will form the basis for sample size calculations for the full trial.

Experience and tolerability from a patient perspective will be assessed by the participant experience questionnaire, completed at the follow-up visit by all participants. The semi-quantitative data will be analysed using SPSS and presented descriptively whilst free text data will be transcribed verbatim to excel spread sheet to derive themes using thematic analysis approach. Semi-qualitative data that are not part of the OpenClinica study database will be analysed via their unique study identifier.

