#### 6.1 ACTIVE INVESTIGATIONAL PRODUCT

The study compares three strategies of care: withdrawal of oral iron, continuation of oral iron, or switching from oral iron to intravenous Iron. All these drugs are normally used in the NHS to treat iron deficiency anaemia. The study does not compare the safety or efficacy of these iron preparations.

- Oral iron has been previously prescribed by the direct care physician (i.e. GP or hospital clinician).
  - At randomisation continuation or discontinuation will be notified in writing to the direct care physician and verbally (via telephone visit).
- IV Iron will be prescribed by the site PI or delegated medically qualified research team member.
  - Local policies will apply.
  - Ferric carboxymaltose or iron sucrose will be permitted, this reflects current clinical practice where different sites use different preparations.
  - The dose and administration time of IV iron will be calculated using both the participant's bodyweight and the haemoglobin level. This is in line with current prescribing practice.
  - NHS emergency/resuscitation facilities are available at each study site.
  - In a suitable clinical setting the participant will receive IV iron infusion according to local policies for the safe administration of IV iron.

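### The adjusted cost, EQ-5D-5L and 15D regressions leave out site, although randomisation is stratified by it and the Hb/ferritin model adjusts for it; the loss is small and conservative

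*Protocol*

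**What the plan says.** Section 9.2 first presents costs, EQ-5D-5L and 15D unadjusted, as means with SDs and medians with interquartile ranges. It then adds regression-adjusted values, "with baseline cost, quality of life values, treatment group and patient demographics as co-variates". Site does not appear, and patient demographics cannot reasonably be read to include it: section 7.1.1 illustrates demographic information with home circumstances and mobility aids.

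Three other places bear on this:

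- Section 5.5.1, on allocation: "Randomisation will be stratified by site, and further balanced using minimisation".
- Section 9.2, on haemoglobin and ferritin: "analysis of covariance with baseline Hb and ferritin level and site as covariates".
- Section 6.1, on why two IV preparations are allowed: "this reflects current clinical practice where different sites use different preparations". Section 9.2 counts as costs "outpatient/day case visits for iv iron administration, costs of blood transfusion and oral iron".

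Section 12.3 mentions a separate Health Economic Analysis Plan, which is not at hand.

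**The concern.** Stratifying by site keeps the arms balanced within each site, so differences between sites largely drop out of the true sampling error of an arm comparison. A model without site does not know this. It leaves the between-site variation in the residual and reports a standard error that is larger than the real one. Section 9.2 avoids this for haemoglobin and ferritin and gives no reason for treating costs and quality of life differently.

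The stakes are modest but real for a pilot. Quality of life is among the primary outcomes proposed for the main trial (S.2), and cost-effectiveness is one of that trial's aims (section 1.2). Less precise adjusted estimates, or an inflated residual SD if someone later uses it for planning, would be an avoidable loss.

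**Working it through.** **Inputs from the protocol.** Four sites (section 5.1.1); "approximately 21 in each NHS site i.e. 7 participants randomised into each study arm" (section 4.1), so 4 × 3 × 7 = 84; 1:1:1 allocation (section 5.5.1); "We will aim to have 20 completed participants in each arm (60 in total" (section 9.1). At the assumed 30% dropout, 84 × 0.70 = 58.8, close to 60. The calculation takes 60 completers, that is 60 / 12 = 5 per arm in each site. The plan states no figure of its own on this point.

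**Assumptions, not in the documents.** Total outcome variance is 1. Site accounts for a share p = 0.05, 0.10, 0.20 or 0.30, with the same site shift in all arms. The within-site correlation between baseline and follow-up is ρ = 0.5. Site effects are drawn at random; with four sites the realised between-site variance (divisor 4) averages q = 0.75p. The covariate list is read as including the baseline value of each outcome.

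**Formulas.** The width of the confidence interval for an arm difference is roughly proportional to the residual SD.

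- Site in the model: residual variance w = (1 − p)(1 − ρ²).
- Site omitted, no site effect at baseline (case A): w + q.
- Site omitted, same site effect at baseline and follow-up (case B): (q + 1 − p) − [q + ρ(1 − p)]² / (q + 1 − p).

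The width ratio, with site to without, is the square root of w over the relevant variance.

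| p | w | Case A variance | Ratio A | Case B variance | Ratio B |
|---|---|---|---|---|---|
| 0.05 | 0.7125 | 0.750 | 0.975 | 0.722 | 0.994 |
| 0.10 | 0.6750 | 0.750 | 0.949 | 0.692 | 0.987 |
| 0.20 | 0.6000 | 0.750 | 0.894 | 0.632 | 0.975 |
| 0.30 | 0.5250 | 0.750 | 0.837 | 0.568 | 0.962 |

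In case A the narrowing is about 3, 5, 11 and 16%. In case B the approximation gives 0.6, 1.3, 2.5 and 3.8%. Simulation, which also counts the three degrees of freedom and averages over the site draws, gives 0.5, 1.0, 2.0 and 3.2%.

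**Sensitivity to the definition of p.** If the realised variance of the four sites equals the whole share (q = p), case A at p = 0.30 becomes √(0.525 / 0.825) = 0.798, a 20% narrowing.

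**Coverage without site.** In case B, coverage of a nominal 95% interval stayed between 94.9% and 96.0%, with no trend in p. In a case A simulation with q = p and 30% random dropout, it was 96.1% at p = 0.10, 97.2% at 0.20 and 97.7% at 0.30; with site in the model it was about 95%.

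**If site explains nothing.** Adding it widens the interval by about 0.2% when completers are balanced. With 30% random dropout, which disturbs the balance, the simulated widths were 1.134 with site and 1.122 without: 1.134 / 1.122 = 1.011, about 1%.

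**The IV product.** This difference acts in one arm only. With site shifts confined to the IV arm, of SD 1 and 2 in outcome SD units, intervals without site were 1.04 and 1.11 times as wide as with site. Coverage without site was 97.0% and 98.2%; with site it was 96.7% and 98.2%. A site main effect therefore recovers some width but leaves the over-coverage almost unchanged. At shifts of 0.5 SD or less, adding site made no practical difference.

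**The case against.** The strongest objection is that the loss may be negligible. The listed covariates include baseline values, and the care use questionnaire covers the preceding three months at both baseline and follow-up (Table 4, Appendix 3). Stable differences between sites would then be largely absorbed, as in case B. This stands, and case B is the likelier case for EQ-5D-5L and 15D.

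Three stronger readings are tempting, and the documents do not support them.

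- A reader might infer that the planned confidence intervals are too wide. Section 9.2 promises 95% intervals for the recruitment and retention measures, not for these regressions. Any excess width also depends on site predicting the outcome.
- A reader might infer that the main trial's sample size will be inflated. Section 9.2 bases it on the distribution of changes and presents these measures unadjusted first. It does not say that a residual SD from these models is carried forward, and adding site would leave the unadjusted SDs as they are.
- A reader might infer that adding site deals with the different IV preparations. They produce a treatment-by-site effect, which a site main effect removes only in part. Nor do the documents say whether costing uses local or common unit costs.

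It can also be said that covariate detail belongs in the Health Economic Analysis Plan. That would answer a silent protocol, but this one gives a list, and a plan that follows it inherits the omission. Lastly, the minimisation variables are not on the list either. That is true, but site is the stratification factor and the one for which section 9.2 sets its own precedent.

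**Conclusion.** The point holds as a minor inconsistency with an easy remedy. The stated covariate list omits the factor by which randomisation is stratified, and the neighbouring model includes it. The consequence is conservative: standard errors and residual SDs somewhat too large, to the extent that site predicts the outcome beyond baseline. Under assumed site shares of 5 to 30% and a within-site baseline correlation of 0.5, the gain in interval width from adding site is about 0.5 to 3% if baseline carries the site effect and about 3 to 16% if it does not. The upper range needs site effects that arise after baseline, which is more plausible for costs than for quality of life. No document gives the site share, so no single figure can be claimed.

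**What to change.** In section 9.2, add site to the covariates of the adjusted cost, EQ-5D-5L and 15D regressions, as a factor with three degrees of freedom, and carry the same list into the Health Economic Analysis Plan. State at the same time that the baseline value of each outcome is a covariate, and name the demographics meant.

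The cost is a short edit in two documents and three degrees of freedom out of about 60 completers. If site turns out not to matter, the loss in width is about 0.2% with balanced completers and about 1% with uneven dropout. To show any cost difference between IV preparations, tabulate IV-arm costs by site descriptively rather than rely on the site term.
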